5. SELECTION AND WITHDRAWAL OF SUBJECTS

5.1 Inclusion criteria

Cohort 1: RDS Patients Who Did Not Have Early Surfactant Instillation

- 1) NICU patient, ≥ 1 hour of age and < 12 hours of age.
- 2) Clinical diagnosis of RDS, with or without chest X-ray data.
- 3) Inspired oxygen $\geq 25\%$ and $\leq 40\%$ to maintain adequate oxygen saturation.
- 4) Not intubated
- 5) Requiring:
 - (a) nasal continuous positive airway pressure (nCPAP), or
 - (b) high flow nasal cannula (≥ 2 L/kg/min) (HFNC), or
 - (c) non-invasive ventilation.

Cohort 2: RDS Patients Post Early Surfactant Instillation

- 1) NICU patient <24 hours of age.
- 2) Intubated, given instilled surfactant at \leq 1hours of age, then extubated within 6 hours.
- 3) Inspired oxygen \geq 25 and \leq 40 % to maintain adequate oxygen saturation.
- 4) Not intubated.
- 5) Requiring: (a) nasal continuous positive airway pressure (nCPAP),or
(b) high flow nasal cannula (\geq 2 L/kg/min) (HFNC), or
(c) non-invasive ventilation.
- 6) Increasing in FiO₂ and/or respiratory support for \geq 1 hour.

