7.2 Efficacy methods

All data will be extracted from each patient's medical record and entered into a case report form. No specific testing is defined. Data to be extracted to assess efficacy is:

- 1) Requirement for Instilled Surfactant to 72 hours of age.

- Number of patients requiring surfactant instillation from randomization to 72 hours of age. Intubation and instillation is indicated if there is a continuing, > 1hour, requirement for >40% inspired oxygen plus continuing positive pressure support to maintain acceptable blood oxygen saturations.

2) Measures of Severity of RDS from Randomization to Surfactant Instillation or 72 hours of age.

- (a) Supplemental oxygen measured as the increase and/or decrease over time.
- (b) Duration of positive pressure respiratory support over time.

3) Duration of RDS to 7 days of age :

- (a) Time from birth to when patient last required >25% oxygen.
- (b) Requiring >25% oxygen for ≥7 days (168 hours) from birth shall be defined as “unresolved RDS”.

4) Incidence of pulmonary complications to 7 days of age

- (a) Occurrence(s) of radiologically or clinically diagnosed pneumothorax, pneumomediastinum, pulmonary interstitial emphysema, subcutaneous emphysema or pneumopericardium.
- (b) Pulmonary hemorrhage defined as gross bleeding from the airway, changes in a chest X-ray consistent with pulmonary hemorrhage and acute deterioration of respiratory function.
- (c) Acute pneumonia defined as acute deterioration of respiratory function accompanied by clinical and chest X-ray findings consistent with bacterial pneumonia and a clinical decision to institute appropriate antibiotic therapy for acute pneumonia.

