9. STATISTICS

9.1 Statistical Methods

ONY, Inc., or its designee, will be responsible for (a) data management, (b) reviewing and validating all information in the clinical report forms, (c) statistical analysis, and (d) generation of the clinical study report. A Statistical Analysis Plan (SAP) providing details of statistical analyses performed after completion of the study will be developed. Prior to locking the database, all data editing will be completed and decisions regarding the evaluability of subject data for inclusion in statistical analyses will be made. The rationale for excluding any data from statistical analyses will be prospectively defined, and classification of all or part of a subject's data as non-evaluable will be documented before the database is locked and the statistical analysis is begun. ONY, Inc., or designee will perform the statistical analysis of the data derived from this study. All analyses will be carried out using SAS version 9.4 (or higher) statistical software (Cary, NC).

Statistical design: This study is a randomized, multiple-center clinical trial designed to assess the superiority of the experimental intervention (aerosolized Infasurf) relative to active control (“usual care”) with regards to the incidence of intubation and instillation of liquid surfactant suspension. A total of up to 200 subjects who received instillation of surfactant for RDS in the first hour of life (“the post-instilled cohort”) and up to 458 subjects who did not receive surfactant at birth who develop RDS in the first hours of life (“the uninstalled cohort”) will be enrolled. Treatment assessment will be done for each cohort separately, that is, this study may be thought of as two individual trials under one protocol.

Stratification: The randomization will be stratified by center and patient cohort and significance tests applied in the analyses will be stratified by center.

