Randomization: Subjects will be randomized to the intervention or active control arm in a 1:1 fashion using a stratified permuted block randomization scheme with variable block sizes of 2 and 4. Randomization lists will be generated by the study biostatistician which will then be used to create an envelope-based system to be used at the individual study sites. Subjects will be included in primary data analyses according to their randomized assignment irrespective of the treatment actually received (intent-to-treat). Exceptions would include those who withdraw their consent to use any of their data prior to subject evaluation.

Accrual. Subjects will be accrued to the study on a first-come basis. The projected accrual is approximately 80 per month, and therefore recruitment is expected to be complete at most 365 days following the study starting point. Subjects will be followed to hospital discharge or 28 days whichever is shorter so total study duration will be approximately 13 months.

Descriptive analyses. Measured outcome variables will be summarized overall and by relevant demographic and baseline variables. Descriptive statistics such as frequencies and relative frequencies will be computed for all categorical variables. Numeric variables will be summarized using simple descriptive statistics such as the mean, standard deviation and range. A variety of graphical techniques will also be used to display data, ex. histograms, boxplots, scatterplots, etc.

Primary efficacy analyses. The primary efficacy analysis will be performed within each cohort separately and is based on a test for superiority of the experimental treatment relative to active control with regards to intubation rate. An overall assessment of the probability of intubation differences across study sites will be done using the Cochran-Mantel-Haenszel test. A one-sided nominal significance level of 5% will be utilized. Additional analyses will be performed utilizing both cohorts of subjects in order to assess differential treatment effects.

Primary safety analyses. All adverse events will be recorded during the study period and then tabulated at the end of the study.

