Interim analysis. A group sequential approach will be utilized in the statistical evaluation of data, with a two interim analyses and the final analysis planned. The interim analyses, which will assist in making the decision of whether or not to stop the trial early for futility, will take place after the study outcome variables are observed in approximately the first 1/3 of evaluable subjects and after approximately 2/3 of evaluable subjects. Assuming increasing recruitment during the months and allowing for data clean up and statistical analysis, we anticipate the interim analysis will be performed at approximately 4 months after enrollment of the first patient. The principal interim analyses will involve the computation of the conditional power pertaining to the test of the primary efficacy outcome, that is, we will compute the probability of rejecting the primary null hypothesis at the end of study given the data observed thus far. In the event of unfavorable trends in the data, the conditional power of achieving a final conclusion of superiority will be much less than the initial planned power of the study for a given point in the alternative parameter space, thus making conditional power a quantitative tool for use in interim decision making. Monte Carlo simulations based on 10,000 iterations will be utilized to compute the conditional power under two difference scenarios: 1) assuming the parameter values utilized for sample size derivation, and 2) assuming the true parameter values are equal to the sample estimates computed from the interim data. Given the uncertainty in the actual values of the parameters, the conditional power associated with the second scenario should be viewed as that which is most informative in decision making. Additionally, 95% confidence intervals will be obtained and used to assess if the values assumed in the planning of the study are much different than those suggested by the data. The conditional power for selected values within the computed confidence intervals may be calculated if deemed potentially informative. Results of interim analyses will be reviewed by the Data and Safety Monitoring Board. After the second interim analysis, sample size may be modified using the method discussed in Gould (1992),⁷ performed in conjunction with an effect size of a 20% decrease in intubation rate.

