9.2 Sample size justification

In order to gauge the adequacy of the proposed sample size, the statistical power based on the proposed superiority analyses described above was determined. Power in this context is defined as the probability of deeming the experimental treatment superior to active control after performing the test for superiority on the study data at the conclusion of the study, done in conjunction with a 5% nominal significance level. For the sake of simplicity, calculations corresponding to the test based on the proposed approach are approximated by those of a simple two-sample binomial test. We assume the intubation probability corresponding to the active control group to be 60%. This is based on an abstract presented at the Pediatric Academic Societies meeting of 2016 in which the incidence of intubation and instillation of surfactant among infants with early RDS requiring 30 - 40% oxygen was 32 of 50, 64%. A clinical meaningful effect in the uninstalled cohort is defined as a 20% decrease (in percentage points) in the intubation rate which equates to a 48% intubation rate. Calculations show a sample size of 229 per group (458 total) in this cohort will result in a test procedure which is associated with power of approximately 80.1%. In the post-instilled cohort, 200 subjects will be enrolled. This will provide approximately 80% power is detecting a 30% decrease in the intubation rate (60% versus 42%).

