9.5 Procedure for revising the analysis plan

If the study biostatistician determines the analysis plan is in need of revision after the study starts, the biostatistician and study chairman will discuss the validity and influence of revision in the evaluation of study data and will then determine if the revision can be conducted. The details of any revisions will be described in the clinical study report for this protocol.

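### Optional gain in efficiency: the center-stratified Cochran-Mantel-Haenszel primary test is valid, but it leaves baseline FiO2 and gestational age, both already collected, unused

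*Combined protocol and SAP*

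**What the plan says.** Section 9.1 analyzes the two cohorts separately, almost as two trials. Randomization is stratified by center and cohort, and "significance tests applied in the analyses will be stratified by center". For the primary outcome, the assessment of intubation "differences across study sites will be done using the Cochran-Mantel-Haenszel test", one-sided at 5%. Baseline variables appear only in the descriptive summaries.

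The same section leaves room for detail: "A Statistical Analysis Plan (SAP) providing details of statistical analyses performed after completion of the study will be developed". Section 9.5 covers later changes, for which "the biostatistician and study chairman will discuss the validity and influence of revision in the evaluation of study data"; it sets no time limit.

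Both candidate covariates are collected:
- **Gestational age** is in the demographic part of the case report form. Sections 5.1 and 5.2 set no gestational-age limit.
- **FiO2** is in the timed Aero-02 respiratory support sheet, used for both arms. Its directions start the log when the infant goes onto support. Support is an entry criterion, so the log begins before randomization.

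Infants enter on 25% to 40% oxygen "to maintain adequate oxygen saturation" (section 5.1). Under section 7.2, intubation and instillation is indicated by a continuing "requirement for >40% inspired oxygen plus continuing positive pressure support to maintain acceptable blood oxygen saturations", lasting more than an hour.

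**The concern.** Entry FiO2 measures how far an infant starts from the oxygen level at which the primary event is indicated, so it is plausibly prognostic. Gestational age is unrestricted and may be prognostic too. If either predicts intubation, a test that ignores it leaves outcome variation unexplained that could be removed without another infant. Each cohort must succeed on its own with about 80% planned power, so a few points are worth having if they cost little.

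Timing also matters. The trial is unmasked (sections 4.2 and 4.3), and the sponsor or its designee handles both data management and analysis (section 9.1). A model chosen after outcomes had been compared by arm could not be shown to be independent of the results.

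**Working it through.** **1. Reproduce the stated power (section 9.2).** Inputs: 229 per arm, 60% versus 48%, one-sided 5%, simple two-sample binomial test. With difference d, mean rate p̄ and n per arm, power = Φ{[(d − c)√n − 1.645√(2p̄(1−p̄))] / √(p1(1−p1) + p2(1−p2))}, where c = 1/n with continuity correction and 0 without.

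- 229 per arm, corrected: [(0.12 − 0.00437)(15.133) − 1.645(0.7048)] / 0.6997 = 0.844, so 80.06%. This is the plan's 80.1%. Uncorrected: 82.6%.
- 100 per arm, 60% versus 42%: 78.0% corrected, 82.0% uncorrected, consistent with the plan's approximate 80%.

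**2. What the documents say about prognostic strength.** Section 9.2 gives one rate, for "infants with early RDS requiring 30 - 40% oxygen was 32 of 50, 64"%, and no gradient by oxygen level or gestational age. Strength must be assumed. If FiO2 is uniform over 25% to 40%, the entry range spans √12 = 3.46 SD. An odds ratio (OR) per SD of 1.25, 1.5 or 2.0 then means 1.25^3.46 = 2.2-fold, 1.5^3.46 = 4.1-fold or 2.0^3.46 = 11-fold odds from bottom to top. OR 2.0 is best read as an upper bound.

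**3. Simulated power, 10,000 trials per setting.** Assumptions: permuted blocks of 2 and 4 within center; 20 centers of unequal size; center SD 0.4 on the logit scale; the two covariates independent and equally strong; 2% of FiO2 values missing and mean-filled; the plan's event rates. Planned: CMH by center without continuity correction. Adjusted: linear model of the 0/1 event on treatment, center, FiO2 and gestational age, HC2 variance, t reference, centers with fewer than 10 infants pooled.

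| OR per SD, both | 229/arm: CMH → adjusted | 100/arm: CMH → adjusted |
|---|---|---|
| 1.0 | 83.8% → 83.8% | 83.1% → 82.9% |
| 1.25 | 83.7% → 84.4% | 83.0% → 83.7% |
| 1.5 | 83.5% → 85.8% | 82.8% → 85.0% |
| 2.0 | 83.0% → 88.9% | 82.5% → 87.9% |

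Over 10, 20 and 30 centers and both cohorts the change is -0.4 to +0.3 points at OR 1.0, +0.4 to +0.8 at 1.25, +1.5 to +2.6 at 1.5 and +4.9 to +6.2 at 2.0. If only FiO2 predicts, it is +0.9 to +1.7 at 1.5 and +2.9 to +3.5 at 2.0. Type I error is 4.5% to 5.5% for the planned test and 4.6% to 5.4% adjusted.

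**4. Analytic check.** The simulated variance ratio, with versus without covariates, is 0.93 to 0.94 at OR 1.5 and 0.84 to 0.85 at OR 2.0. Replace n by n divided by the ratio in the uncorrected formula. For 229 per arm, 229/0.94 = 243.6 gives 84.6% (+2.0 points) and 229/0.85 = 269.4 gives 87.7% (+5.1). For 100 per arm the gains are +2.1 and +5.2. These agree with step 3.

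**5. What else moves the answer.**
- *Simulation noise.* A smaller repeat (1,500 trials, standard error 0.3 to 0.8) gave -0.5, +2.3 and +5.1 points (229 per arm) and -0.7, +1.8 and +8.0 (100 per arm) at OR 1.0, 1.5 and 2.0. Hence the rounding to -1 to 0 at no effect and to about +5 or more at OR 2.0.
- *Variance estimator.* HC3 in place of HC2 gives -1.7 to -0.8 points at OR 1.0.
- *Method.* Adding FiO2 half and gestational-age half as further CMH strata (20 equal centers, 6,000 trials) changed power by -4.8 to +2.1 points at 229 per arm and by -14.2 to -7.0 at 100 per arm, as the variance explained (R²) rose from 0 to 0.28.
- *Pooling.* With the unequal center sizes assumed, pooling centers under 10 merges about 23% of infants in the 200-infant cohort at 20 centers and about 49% at 30.

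**The case against.** The strongest reply is that nothing is broken. The planned test holds its level and, in these simulations, has 82.5% to 83.8% power, above the roughly 80% that section 9.2 aims for. The gain rests on prognostic strengths that the documents do not give. The link from entry FiO2 to the event is looser than the thresholds suggest: section 7.2 says when intubation is indicated, but usual care has no protocol-driven interventions (section 6.1) and other treatment is unrestricted (section 6.2). One odds ratio for both cohorts is a further assumption, since the second cohort is also selected on rising oxygen or support. The adjusted model also needs things that CMH does not: a rule for missing covariates, pooling of small centers and a choice of variance estimator.

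Most of this stands, and it makes the change optional. It does not remove the case for adjusting. If the covariates predict nothing, the loss with HC2 is under 1 point; if they are moderately prognostic, the gain comes without more infants. An adjusted analysis kept only as sensitivity analysis would leave the primary test with none of that gain.

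A reader might infer that the planned test is invalid or the trial underpowered for want of adjustment. Steps 1 and 3 show neither. A reader might also expect a gain of about 6 points. That needs OR 2.0 per SD for both covariates, which nothing in the documents supports.

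**Conclusion.** This is an optional efficiency improvement, not an error. The center-stratified CMH test is valid and the stated power stands without adjustment. Under the assumptions listed, prespecified adjustment changes power by roughly -1 to 0 points if neither covariate predicts intubation, about +0.5 at OR 1.25 per SD for both, +1.5 to +2.6 at 1.5, and about +5 or more only at 2.0. Prognostic strength is the main driver, but method, variance estimator, number of centers and cohort also move the figure, so it cannot be read as depending on prognosis alone. Confidence is medium: the facts about the plan are clear, the size of the gain is not.

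**What to change.** In the SAP still to be developed, and before any outcome data are compared by arm:

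1. **Primary analysis, each cohort.** Specify a covariate-adjusted risk difference from a linear model of the primary event on treatment, center, FiO2 and gestational age (both continuous), with HC2 variance and a t reference, at the planned one-sided 5%. Pool centers with fewer than 10 infants in that cohort; if the pooled stratum holds a single infant, merge it with the next smallest center. Keep the center-stratified CMH test as sensitivity analysis. Do not add the covariates as CMH strata.
2. **Baseline FiO2.** Use the last Aero-02 value at or before randomization in both arms. Add the randomization time to the case report form, because the envelope procedure in section 4.8 records none. Do not use the procedure-note values in Appendix A, which are timed before aerosol start in one arm and at randomization in the other. Reconcile section 13.1, where respiratory data begin at randomization, with the Aero-02 directions, where they begin at start of support.
3. **Missing covariates.** As a stated exception to section 9.4, replace a rare missing baseline value by the cohort mean over both arms. Outcomes stay unimputed. Dropping 2% of infants instead would cost 0.5 to 1.0 points at OR 1.0 to 1.5.
4. **Interim analyses.** Base conditional power on the same test. For the scenario "assuming the parameter values utilized for sample size derivation", use the section 9.2 rates with no covariate effect, and tell the board that this understates conditional power if the covariates are prognostic. For 229 per arm, one third of the information and interim z = 0, it gives 54.2%, against 56.8% at a variance ratio of 0.94 and 61.2% at 0.85.

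**Cost:** SAP wording, one recorded time, one exception to section 9.4 and some re-programming; no extra patients. **Downsides:** under 1 point of power if the covariates predict nothing (up to about 1.7 with HC3), and coarser center adjustment through pooling, about 23% of infants in the 200-infant cohort if there are 20 centers of unequal size.

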4.3 Bias avoidance

Randomization codes predetermined using small, but variable, blocks to assure that each site will have approximately a 1:1 ratio of aerosolized and usual care participants. The study will be unblinded because it is impossible to blind staff to aerosolization of Infasurf. Visual evidence of Infasurf administration is obvious to all care givers both during and after the therapy. Also it is not ethically justified to subject the “usual care” group of fragile NICU patients with RDS to aerosolization with a saline placebo when there is only the potential for complications and none for benefit.

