4.8 Randomization Codes

Each participating site will be provided a separate sequential randomization code in opaque envelopes. The blocks will be small but the size of the blocks will be confidential so investigators cannot predict assignment. Patient assignment will be to the study arm indicated by the next envelope in sequence opened after consent is obtained. The study sponsor will generate the randomization code for each site using the Moses-Oakford algorithm.⁶

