15 APPENDICES

APPENDIX A

Intervention Notes Formats

Initial Aerosol Procedure Note

Date Time: Patient was randomized to the Aerosolization Group in the Aerosolized Infasurf Trial in the {never treated} {previously instilled} cohort. The initial aerosolization was started at ___:___ hours and was completed at ___:___ hours. A total of ___ mL of Infasurf was aerosolized. The Inspired O₂ prior to starting the aerosol was ___%. The aerosolization {was} {was not} completed. There {was no} {was an} adverse event during the aerosol delivery. {If present describe in detail}.

Repeat Aerosol Procedure Note

Date Time: A repeat aerosolization was started at ___:___ hours and was completed at ___:___ hours. A total of ___ mL of Infasurf was aerosolized. The Inspired O₂ prior to starting the aerosol was ___%. The aerosolization {was} {was not} completed. There {was no} {was an} adverse event during the aerosol delivery. {If present describe in detail}.

Usual Care Procedure Note

Date Time: Patient was randomized to the Usual Care Group in the Aerosolized Infasurf Trial in the {never treated} {previously instilled} cohort. The Inspired O₂ at the time of randomization was ___%.

Aerosolized Infasurf Trial Case Report

1. Identity Data

Last Name _____

Date of Birth ____/____/____

Time of Birth ____:____

Hospital # _____

Study # _____

Consent # _____

Strata A B

Rx Group Usual Care Aerosolized

2. Demographic Data

Sex M F

 Single MultA MultB MultC

Birth Wt _____grams

Gestational Age ____wks ____days

Maternal Steroids N <12 hrs >12 hrs

Delivery: Vaginal C-Section

APGAR ____ 1min ____ 5 min

Intubated in DR Y N

Surfactant in DR Y N

3 A. 1st Aerosolization Procedure Data

Date		
Start time		
End time		
Patient Age (hrs)		
Dose (mL)		
Aerosol duration (min)		
Mode of Support		
FiO2	Pre	
	30 min	
	60 min	
	90 min	
	120 min	
	180 min	
	240 min	
Aersolization interrupted		

3 B. 2nd Aerosolization Procedure Data

Date		
Start time		
End time		
Patient Age (hrs)		
Dose (mL)		
Aerosol duration (min)		
Mode of Support		
FiO2	Pre 1	
	30 min	
	60 min	
	90 min	
	120 mins	
	180 min	
	240 min	
Aersolization interrupted		
Full dose given		

3 C. 3rd Aerosolization Procedure Data

Date		
Start time		
End time		
Patient Age (hrs)		
Dose (mL)		
Aerosol duration (min)		
Mode of Support		
FiO2	Pre 1	
	30 min	
	60 min	
	90 min	
	120 mins	
	180 min	
	240 min	
Aersolization interrupted		
Full dose given		

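### Section 4.8 relies on block sizes being confidential, but section 9.1 of the same protocol prints them (2 and 4); a site that tallies could then know some assignments for certain, about 6–13% under assumed block mixes.

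*Combined protocol and SAP*

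**What the plan says.** Three sections of the combined protocol and SAP describe the blocks.

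- Section 4.3: "Randomization codes predetermined using small, but variable, blocks", with no sizes given.
- Section 4.8: "the size of the blocks will be confidential so investigators cannot predict assignment".
- Section 9.1, Randomization: a "stratified permuted block randomization scheme with variable block sizes of 2 and 4".

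Other provisions decide whether a site could keep a tally.

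- Masking (4.3): "The study will be unblinded because it is impossible to blind staff to aerosolization of Infasurf".
- Envelopes (4.8): "Each participating site will be provided a separate sequential randomization code in opaque envelopes". The next envelope is opened after consent.
- Strata (9.1): "The randomization will be stratified by center and patient cohort and significance tests applied in the analyses will be stratified by center".
- Chart notes (Appendix A): the usual care note reads "Patient was randomized to the Usual Care Group in the Aerosolized Infasurf Trial in the {never treated} {previously instilled} cohort", and the note for the first aerosol treatment likewise records arm and cohort.

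Nothing in the document withholds section 9.1 from the sites.

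**The concern.** Section 4.8 gives one reason why investigators cannot foresee the next assignment, and section 9.1 removes it. The rest of the protocol is addressed to site staff (eligibility, dosing, stopping, data sheets), so they would ordinarily hold the whole document.

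Concealment matters more here because masking gives no protection. Entry leaves some discretion: section 5.1 accepts a clinical diagnosis with or without a chest X-ray, inspired oxygen anywhere from 25% to 40%, and an age window of hours. Someone certain of the next arm could let that affect which family is approached, or when. Opening the envelope after consent does not prevent this, because the knowledge comes from the tally and not from the envelope.

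**Working it through.** The plan states no predictability figure, so there is none to reproduce.

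**Inputs.** Sizes 2 and 4 (9.1); 1:1 allocation (4.2); strata of center by cohort (9.1); up to 458 and 200 infants (9.1). The plan gives neither the mix of sizes nor the number of centers. I assume that a share w of blocks has size 2, with w = 1/2 as base and 1/3 to 2/3 as range, and 10, 20 or 40 equal centers. The reader sees every earlier assignment in the stratum but not where blocks begin.

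**When an assignment is certain.** A block of 2 never gets more than one out of balance. A block of 4 has 6 arrangements, and 2 of them (AABB, BBAA) open with the same arm twice. The tally reaches two only then, and the next two assignments are fixed.

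**Long lists.** Share certain = (1−w)(2/3) / [2w + 4(1−w)].

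- w = 1/3: 0.444/3.333 = 13.3%
- w = 1/2: 0.333/3 = 11.1%
- w = 2/3: 0.222/2.667 = 8.3%

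**Finite strata.** Sum, over positions, the probability of being third or fourth in a block of 4, divide by 3, then divide by the stratum size n. For n = 6 and w = 1/2, the probabilities at positions 3 to 6 are 1/2, 1/2, 1/4 and 1/4. So (1.5/3)/6 = 8.3%.

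| n | w = 1/3 | w = 1/2 | w = 2/3 |
|---|---|---|---|
| 5 | 10.4% | 8.3% | 5.9% |
| 6 | 9.9% | 8.3% | 6.2% |
| 12 | 12.1% | 9.9% | 7.3% |
| 40 | 12.9% | 10.7% | 8.0% |

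Very small strata give less: at w = 1/2, none with two infants and (0.5/3)/3 = 5.6% with three.

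**Counts of certain assignments (10 / 20 / 40 centers).**

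| Cohort | w = 1/3 | w = 1/2 | w = 2/3 |
|---|---|---|---|
| 458 | 59.5 / 57.9 / 54.8 | 49.4 / 47.9 / 45.0 | 36.9 / 35.7 / 33.2 |
| 200 | 25.1 / 23.0 / 20.7 | 20.7 / 19.2 / 16.7 | 15.4 / 14.2 / 11.9 |

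**What disclosure adds.** Suppose a site is told only that blocks are small and variable, and assumes equally likely sizes 2, 4 and 6. Per block of 4, an imbalance of two occurs 1/3 times and the lagging arm always follows. Per block of 6, it occurs 0.8 times (0.4 after two infants, 0.4 after four), and the lagging arm follows 0.4 × 3/4 + 0.4 × 1 = 0.7 times. The site's belief is (0.333 + 0.7)/(0.333 + 0.8) = 91%. Adding size 8 (1.314 occurrences, 1.057 followed by the lagging arm) gives 2.090/2.448 = 85%. Section 9.1 raises this to 100%.

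**Overall guess accuracy.** Always guess the arm that is behind, and toss a coin when level. Expected correct guesses are 1.5 per block of 2. Per block of 4 they are (1/3)(2.5) + (2/3)(3) = 2.833. At w = 1/2 the long-run rate is (1.5 + 2.833)/6 = 72.2%. Simulation of 3,000 lists gives 67.5% at n = 5, 71.6% at 12 and 72.1% at 46. A Bayesian guesser who knows the sizes scores the same.

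**The case against.** The strongest objection is that disclosure yields no extra correct guesses. Because the true sizes are 2 and 4, the lagging arm always follows an imbalance of two, printed or not. Predictability comes from small blocks within center in an unmasked trial, and 4.3 and 4.8 already reveal those. This stands, and it limits the weight of the point: what changes is a belief of roughly 85–91% becoming certainty.

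It is also fair that opaque envelopes, opening after consent, first-come accrual and short age windows limit what a site could do, and that nothing shows staff would act on a prediction. The percentages depend on an unstated mix: a 1/4 share of size-2 blocks gives 14.3% in long lists and a 4/5 share gives 5.6%.

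One could read 4.8 as hiding only the size of each successive block, with 9.1 listing the possible sizes. That does not rescue the stated aim. Knowing that no block exceeds 4 is enough to make the next two assignments certain at an imbalance of two.

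**Conclusion.** The concern holds: the two sections contradict each other, and the safeguard named in 4.8 fails for anyone who reads 9.1. If one third to two thirds of blocks are of size 2 and strata hold at least five infants, about 6–13% of assignments become certain to a reader with a complete tally. With 10 to 40 equal centers that is about 33–60 of 458 and 12–25 of 200. These counts rest on assumed mixes and center numbers. Overall guess accuracy stays at about 67–72%, the envelope procedure still operates, and no effect on type I error is claimed. The text should be corrected, but this is not a fatal flaw in the design.

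**What to change.** Delete the sizes from section 9.1, describe the blocks only as small and variable, as 4.3 already does, and record the sizes in a restricted randomization document that sites do not hold. Sections 4.8 and 9.1 then agree, and no assignment can be deduced with certainty from an imbalance of two. The cost is one phrase and one controlled document; randomization, analysis and sample size are unchanged. Tallying would still give a better-than-even guess.

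The document does not show whether sites have received 9.1; section 1.6 leaves the principal investigators still to be chosen. Only if sites already hold it should the unused envelopes be regenerated with different, undisclosed sizes. As an illustration, an equal mix of 4, 6 and 8 would hold certain assignments to about 2.5% or less even if it became known, with guess accuracy of about 62–68%.

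The price is slightly more imbalance within centers. Under the center-stratified test (normal approximation, no continuity correction) with 40 equal centers, power moves from 82.40% to 82.27% in the 458 cohort and from 80.62% to 80.07% in the 200 cohort. With strongly unequal centers it moves from 82.11% to 81.85% and from 80.22% to 79.36%. The plan's own 80.1% for the 458 cohort reproduces with a continuity correction (80.06%), so only the differences should be read here.
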